- The subgroup of participants with influenza A infection is identified as a key subgroup for whom the benefit is expected to exceed that of the overall group randomized (i.e., the treatment effect for those with influenza A is expected to be greater than for with influenza B infection) (see section C.). Power is estimated for the subgroup with influenza A.
- Outcomes other than the primary endpoint are divided into key secondary endpoints, supportive efficacy endpoints, and safety endpoints. The three key secondary endpoints are listed in terms of their importance.

B. Protocol summary and history

FLU-IVIG is a randomized, double blind multicenter, international clinical trial. Hospitalized patients with a National Early Warning (NEW) score of 2 or greater will be randomized in a 1:1 allocation ratio to either IVIG plus standard of care (SOC) therapy or to placebo for IVIG (a comparable volume of normal saline) plus SOC, and followed for 28 days. A total of 320 adult patients were to be enrolled over multiple influenza seasons. A schematic of the design is given below.

FLU-IVIG Design
Hospitalized Adults with Influenza A or B

The primary endpoint is an ordinal outcome at Day 7 that has 6 mutually exclusive categories:

1. Death
2. In the intensive care unit (ICU);
3. Non-ICU hospitalization, requiring supplemental oxygen;
4. Non-ICU hospitalization, not requiring supplemental oxygen;
5. Discharged, but unable to resume normal activities; or
6. Discharged with full resumption of normal activities.

Sample size was estimated assuming the following:

- A proportional odds model would be used to compare the IVIG and placebo groups for the primary ordinal outcome.⁴
- Type 1 error of 0.05 (2-sided) and power=0.80 to detect an odds ratio of 1.77 (an odds ratio greater than 1.0 corresponds to a more favorable response to IVIG than placebo).

For the primary analysis, in addition to a treatment indicator, the model will include indicators for whether the participant was enrolled in the ICU or general ward and whether oxygen was required, and will be stratified by geographic region.

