Sample size for the primary objective (N=320; 160 per group) assumed equal allocation of participants to each treatment, type 1 error of 0.05 (2-sided), power=0.80 to detect an odds ratio of 1.77

Category percentages assumed in the design and given in the protocol are shown below in Table 1 for the primary ordinal outcome.

In the discussion that follows, unless otherwise stated, the numbers shown for both treatment groups combined include the 16 participants from the IVIG pilot study. These results are referred to as “FLU IVIG Pooled Outcome Data”.

Table 1

Outcome at Day 7	Percent in Each Category	
	IVIG	Placebo
Death	1.0	1.8
ICU (for FLU 003, assumed those ventilated were in the ICU)	2.1	3.6
Non-ICU hospitalization, O ₂	9.9	15.6
Non-ICU hospitalization, no O ₂	10.3	14.1
Discharged, not back to normal activities	38.4	39.0
Discharged, back to normal activities	38.2	25.8

As previously mentioned, the pooled FLU IVIG outcome data at day 7 after 170 participants were enrolled are similar to pooled data used in the design (see Table 2 below).

Table 2

Outcome at Day 7	Percent in Each Category	
	FLU IVIG Pooled Outcome Data (N=170)	Average of Design Estimates for the IVIG and Placebo Groups
Death	1.8	1.4
ICU	7.1	2.9
Non-ICU hospitalization, O ₂	10.6	12.8
Non-ICU hospitalization, no O ₂	7.6	12.2
Discharged, not back to normal activities	35.9	38.7
Discharged, back to normal activities	37.0	32.0

Pooled FLU IVIG outcome data (category percentages) at day 7 for 220 participants with influenza A infection as of April 30, 2018 are also similar to the overall category percentages above (see Table 3).

Table 3

Outcome at Day 7	FLU IVIG Pooled Outcome Data for Participants with Influenza A Infection (N=220)
Death	1.4
ICU	4.6
Non-ICU hospitalization, O ₂	10.5
Non-ICU hospitalization, no O ₂	8.2
Discharged, not back to normal activities	35.5
Discharged, back to normal activities	40.0

We assume that 232 of the participants ultimately randomized to FLU IVIG will be infected with influenza A. Assuming the design assumptions stated in the protocol and given in Table 1, with 232 participants, power is 0.67 to detect an odds ratio of 1.77 at the 0.05 level of significance (2-sided). An odds ratio of 1.95 can be detected with power=0.80 with 232 participants. The IVIG and placebo category percentages for participants with influenza A infection corresponding to an odds ratio of 1.95 are given in Table 4.

Table 4

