- If central laboratory results are negative or indeterminate for influenza strain/subtype, the local laboratory result will be used for classifying strain/subtype.
- Influenza vaccination was recorded differently on different versions of the baseline case report form. Participants will be considered as vaccinated if they report being vaccinated in the past 6 months or report being vaccinated in the season of their enrollment.
- IVIG lot will be imputed for participants assigned to placebo using the lot of the closest (in time) enrolled participant who received IVIG at that site.
- For the risk score for hospitalization or death at day 7, the following baseline covariates will be considered: age, gender, race/ethnicity, geographic region, duration of symptoms prior to enrollment, status at enrollment (ICU, general ward on O₂, general ward not on O₂), vaccination in current season, influenza strain, comorbidities (see above), other conditions (see above), and season of enrollment. The score for each participant will be determined using a logistic model that includes participants from both treatment groups.

The interaction between each subgroup and treatment will be assessed with expanded proportional odds models. Terms for each subgroup and a cross-product term with treatment will be added to the proportional odds model described above for the primary analysis. Interaction p-values for age, duration of symptoms, risk score for hospitalization or death at day 7, and NEW score will be based on the measured variable (1 df) not the categorical variable.

G. Secondary Endpoints

Some new secondary efficacy endpoints were defined, some in the protocol were dropped, and some are now defined as supportive. Reasons for this are:

- Approximately 40% of participants were discharged by day 3.
- The NEW score at day 3 was only determined for hospitalized participants. Thus, measuring change in NEW score at day 3 (as originally defined in the

protocol) is potentially biased due to missing data.

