- The NEW score encompasses several factors that have been included as outcomes in recent influenza trials (e.g., normalization of respiratory rate and oxygen saturation, or clinical stability/clinical resolution that also considers temperature, heart rate, and systolic blood pressure).^{5,6,7} Considering this and the large number of participants discharged in the first 3 days, a second ordinal outcome with 5 categories was defined based on day 3 outcomes that includes the NEW score and does not consider whether participants discharged have resumed normal activities. The latter change was made because the outcome is assessed at day 3, shortly after the acute illness, when resumption of normal activities is less likely. The categorization by the participant of resumption of normal activities was also the most subjective component of the primary ordinal endpoint.

Key Secondary Endpoints

These 3 key secondary outcomes and the supportive efficacy outcomes will be used to compare all randomized participants in the primary analysis set of participants (see D. for definition) and in those with influenza A infection who are in the primary analysis set.

- Five category ordinal outcome on day 3:
 - Death
 - ICU
 - Non-ICU hospitalization, NEW score ≥ 3
 - Non-ICU hospitalization, NEW score < 3
 - Discharged
- Primary 6-category ordinal outcome on day 3
- Favorable outcome at day 7 taking in to account enrollment from the ICU or general ward (also referred to as a sliding dichotomy⁸) defined as:
 - ICU at enrollment to general ward or discharge before day 7
 - General ward at enrollment to discharge before day 7

Power Considerations for the Key Secondary Endpoints:

- For the 5-category ordinal outcome at day 3, an odds ratio of 1.78 can be detected with power = 0.80 at the 0.05 level of significance (2-sided).
- For the 6-category primary ordinal outcome at day 3, power is 0.80 to detect an odds ratio of 1.78.
- For the favorable outcome at day 7, power is 0.80 to detect a 12.5% absolute difference in the percentage with a favorable outcome at day 7 (86% versus 73.5%). For both treatment groups combined, approximately 80% have a favorable outcome at day 7.

The percentage of participants in the 5- and 6-category ordinal outcomes described above and that are basis for power estimates are given in Table 5 for both treatment groups combined as of May 23, 2018.

Table 5

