If a NEW score is not available on Day 3, the last available follow-up NEW score will be used.

For the favorable outcome on Day 7, for the 4 participants who are missing the primary outcome on Day 7, it is presumed that they did not die or were re-hospitalized following discharge, i.e., they will be considered as having a favorable outcome.

H. Supportive Efficacy Endpoints

The following efficacy outcomes are defined as supportive:

- Time to discharge
- Time to death
- Percentage alive and out of the hospital at day 28
- Change in nasopharyngeal viral load from baseline to day 3
- Change in HAI titers from baseline to day 1, 3 and 7
- Percentage dying or requiring re-hospitalization after discharge
- Percentage with a diagnosis on or after the day of randomization and before the day 28 visit developing acute respiratory distress syndrome, acute renal failure, sepsis, pneumonia, enteritis or bronchitis (considered individually and also any of the diagnoses)
- Ordinal outcome on day 14
- Percentage alive and out of the hospital at day 14
- Resumption of normal activities at day 14.
- Ordinal outcome on day 28

Analysis Considerations for Supportive Efficacy Outcomes

Kaplan-Meier curves will be used to summarize the time to discharge and time to death, overall and through 7 days. The median number of days from randomization to discharge will be estimated. Deaths during hospitalization will be censored after day 28 (or day 7) for analyses of time to discharge. A logrank test will be used to compare treatment groups.

For participants who experienced multiple hospitalizations during follow-up, the time to the last discharge before day 28 will be considered. As the visit window for the day 28 visit extends to day 35, events after day 28 but prior to the final visit will be included in these analyses.

The difference between the IVIG and placebo group for change in log-transformed nasopharyngeal viral load from baseline to day 3 will be summarized using stratified analysis of variance with baseline viral load as a covariate. Viral loads vary by subtype. Therefore, strata will be defined by influenza virus subtype (H1N1, H3N2, or B) as well as geographic region. In these analyses, levels below 75 copies, the lower limit of detection, will be imputed as 75 copies. For this analysis, deaths (currently one

participant) on or before day 3 will be excluded, as will participants with undetectable RNA.

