The IVIG and placebo group will also be compared for the percentage with undetectable viral RNA at day 3 using logistic regression with baseline viral load as a covariate and geographic region and influenza subtype as stratifying factors. For this analysis, exclusions will be as per the previous paragraph; however, participants dying on or before day 3 (currently one participant) will be included in these analyses and considered as having detectable RNA.

Ordinal outcomes will be summarized using a proportional odds model as described for the primary ordinal outcome (see E.).

Binary outcomes will be summarized with logistic models that are stratified by geographic region and include indicators for the participant's clinical status at entry (ICU, general ward on supplemental oxygen, general ward not on supplemental oxygen), and an indicator for whether the participant was in the IVIG pilot trial (FLU 005) or the FLU-IVIG trial (FLU 006).

Reference viruses used for HAI titers changed over the course of the study corresponding to the circulating viruses. Longitudinal random effects models stratified by subtype (H1N1, H3N2, B) will be used to estimate differences in log-transformed HAI titers between the IVIG and placebo group at days 1, 3 and 7. Baseline HAI levels will be included in these models as a covariate. Each HAI titer assessed will be used to compare the two treatment groups. In addition, analyses specific to the virus of infection, will be carried out. For participants infected with H1N1, A/California/2009 and A/Michigan/2015 will be used; for those infected with H3N2, A/Hong Kong/2014, A/Switzerland/2013 and A/Texas/50/2012 will be used; and for those infected with influenza B virus, B/Phuket/2013, B/Brisbane/2008 and B/Massachusetts/2012 will be used.

I. Safety Endpoints

Targeted symptoms are collected at baseline day 3 and day 7. Unsolicited grade 3 or 4 adverse events are collected on days 1-3, 7, 14, and 28. SAEs are collected throughout the 28 day follow-up. The following will be summarized:

- Percentage of participants for whom infusion was interrupted.
- Percentage of participants with adverse events of grade 3 or 4 severity.
- Percentage of participants with a serious adverse event (SAE).
- Percentage with a composite outcome of death, SAE, infusion interruption, or any grade 3 or 4 adverse event.
- Percentage of participants with each targeted symptom on day 3 and on day 7

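### Time to discharge (supportive endpoint): stratify the log-rank test by clinical state at entry and report a matching Cox ratio with 95% CI

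*SAP*

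**What the plan says.** SAP section H (Analysis Considerations for Supportive Efficacy Outcomes) plans Kaplan-Meier curves for time to discharge and time to death, overall and through 7 days, and a median time to discharge. It then states: "A logrank test will be used to compare treatment groups". In-hospital deaths are censored only after day 28 (or day 7). No strata, covariates, ratio or confidence interval are named.

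Elsewhere the SAP brings in entry state:

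- Primary analysis (SAP I.B): "the model will include indicators for whether the participant was enrolled in the ICU or general ward and whether oxygen was required", with stratification by region.
- Supportive binary outcomes (SAP H): "Binary outcomes will be summarized with logistic models that are stratified by geographic region". The same sentence adds indicators for entry state and for pilot versus main trial. These outcomes include being alive and out of hospital at days 14 and 28.
- Key secondary endpoint (SAP G): "Favorable outcome at day 7 taking in to account enrollment from the ICU or general ward".
- Risk score (SAP F): "For the risk score for hospitalization or death at day 7, the following baseline covariates will be considered". The list that follows includes the three-level status at enrollment.

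Not every model does so. The day-3 undetectable-RNA model uses baseline viral load, region and subtype.

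Protocol 6.1 plans Cox models for time to death and time to discharge, without naming strata. SAP H does not mention them, and their removal is not among the exceptions to the protocol listed in SAP I.A.

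**The concern.** Discharge status at a fixed day is analysed with adjustment for entry state, while the closely related time to discharge is compared without it. The SAP names strata for viral load, adverse events and laboratory changes, so silence here reads as unstratified. Randomization is stratified by clinical site only (protocol 3.5), so the arms are not balanced on entry state by design.

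An unstratified log-rank test keeps its type I error. What is at stake is efficiency: if patients from the ICU leave hospital much later than ward patients, pooling them dilutes the comparison. The smaller unstratified ratio is then a marginal rather than a conditional estimate, not a biased one. A second, smaller matter is that section H on its own yields curves, a median and a p-value, but no between-group effect size with a confidence interval.

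**Working it through.** **The plan's own figure.** The documents give no power, event count or ratio for time to discharge. The nearest stated figure is the primary sample size. The Whitehead formula, N = 12(z_α + z_β)² / {ln(OR)² (1 − Σ p̄³)}, with SAP Table 1 and OR 1.77, gives N = 319.2 and power 0.801 at 320. This reproduces the planned 320 but says nothing about the log-rank test.

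**Is entry state likely to be prognostic?** There is only indirect evidence. The net decline per day is ln(day-3 share / day-7 share)/4, with day 3 from Table 5 (N=323) and day 7 from Table 3 (influenza A, N=220):

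- ICU: ln(6.5/4.6)/4 = 0.086
- Ward on oxygen: ln(21.4/10.5)/4 = 0.178
- Ward without oxygen: ln(30.0/8.2)/4 = 0.324

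The ratio is 0.27/0.55/1. With Table 2 (N=170) for day 7 the values are −0.02, 0.176 and 0.343, so ICU occupancy does not fall. These are net occupancies in different participant sets and concern state at day 3, not at entry. They support an ordering and are not hazard estimates.

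**Simulation of the log-rank test.**

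- From the documents: n = 308, 1:1 allocation, two-sided 0.05, 42% discharged by day 3 (Table 5), in-hospital deaths kept at risk to day 28.
- Assumed: exponential discharge times rounded up to whole days; discharge ratio 1.40; in-hospital deaths 0% or 2%; relative rates ICU/oxygen/no oxygen of 0.5/0.75/1 (mild), 0.3/0.6/1 (moderate) and 0.2/0.5/1 (strong); entry mix 15/45/40% or 7/48/45%.
- 4,000 trials per scenario; 10,000 for type I error.

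Power, unstratified then stratified by entry state:

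| Prognostic strength | No deaths, ICU 15% | No deaths, ICU 7% | 2% deaths, ICU 15% | 2% deaths, ICU 7% |
|---|---|---|---|---|
| Mild | 0.79, 0.82 | 0.81, 0.83 | 0.65, 0.69 | 0.65, 0.67 |
| Moderate | 0.71, 0.82 | 0.74, 0.82 | 0.61, 0.69 | 0.63, 0.69 |
| Strong | 0.64, 0.81 | 0.70, 0.83 | 0.55, 0.69 | 0.56, 0.67 |

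Further results:

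- Type I error: 0.049–0.051 unstratified, 0.048–0.053 stratified.
- Gain at ratio 1.2: 1–3, 2–7 and 4–10 points (mild, moderate, strong). At ratio 1.6: 0–2, 3–6 and 6–10. In the 7-day window at 1.40: 1–2, 4–6 and 6–10.
- Rates 0.27/0.55/1 with entry mix 8/31/61% (Table 5 extrapolated back to day 0), ratio 1.4: 0.69 vs 0.81 without deaths, 0.59 vs 0.67 with 2% deaths.
- Entry state not prognostic: stratifying costs 0–1.2 points.
- Mean ratio at true 1.40, ICU 15%, no deaths: 1.38, 1.34 and 1.31 unstratified (mild, moderate, strong); 1.40 from the stratified Cox model. The 95% CI is a factor of about 1.26 either side.

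**A different set of assumptions.** With deaths of 10/3/1% by entry state and other entry mixes and rates, power at 1.4 moves from 0.64 to 0.68, 0.54 to 0.67 and 0.45 to 0.68. As a check on the method, one stratum in continuous time without deaths gave 0.845, against 0.836 from the Schoenfeld formula with 305 events.

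**P-value against CI.** These figures come from 500 trials at each of ratios 1.3 and 1.4, with assumed region and pilot splits of no effect. A log-rank test and a Cox model stratified the same way disagree at the 5% level in 1.2–1.4% of trials. Adding region and pilot to the Cox model only raises this to 3.8–4.2%. An unstratified log-rank test beside a stratified Cox model disagrees in 18–20%.

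**Time to death.** 1.8% of 170 is 3 deaths by day 7. With an assumed 6 to 12 deaths by day 28, the 95% CI factor exp(1.96 × 2/√d) is 4.95 to 3.10, so stratifying matters little.

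**The case against.** The strongest case is that nothing here is wrong. The unstratified test is valid and is the natural companion to marginal Kaplan-Meier curves and medians. After the change, the p-value and ratio would be conditional while the curves stay marginal. The protocol already plans Cox models, and adjusted analyses of discharge status exist at days 7, 14 and 28. All of this stands and limits the practical loss, but neither document names strata for the Cox models, so the improvement is not already supplied.

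The size rests on assumptions, and the pooled totals do not favour strong heterogeneity. With 42% discharged by day 3 and one constant hazard, day-7 discharge would be 1 − 0.58^(7/3) = 71.9%. The simulated scenarios give 68–72%. Observed values are 72.9% (Table 2) and 75.5% (Table 3), which sit nearest the mild or no-effect end. Sampling error of about ±6 to 7 points and the possibility of rising hazards mean that heterogeneity cannot be ruled out, but the larger gains are not to be expected with confidence.

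The simulation also simplifies the endpoint. The SAP uses the last discharge for readmitted patients and counts events up to the final visit. Power in the influenza A subgroup was not computed. The gains assume a common ratio across entry states; with a larger effect in sicker patients (1.8/1.6/1.2), stratifying lost at most about 2 points.

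The 18–20% disagreement arises only if a stratified Cox model is paired with an unstratified test, a pair neither document plans. It is a reason to match the two, not a criticism of the present text. Finally, entry state alone is not the full adjustment set of the neighbouring models, but crossing it with region could leave sparse ICU strata.

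**Conclusion.** The point holds as an optional improvement to a supportive endpoint. Section H names no strata for the log-rank test, although the SAP itself treats entry state as relevant to leaving hospital. At n = 308 and an assumed ratio of 1.40, stratifying gains about 2–4, 6–11 or 11–17 points of power for mild, moderate or strong prognostic effect, and costs about 1 point if there is none. Entry mix, rates by entry state, deaths by state and the treatment ratio are all assumed, so the direction is firmer than the size. Validity, the primary analysis and the sample size are untouched. I took the text of section H as complete on this test; part of section E was not available to me, but it is unlikely to define strata for section H.

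**What to change.** Add two sentences to SAP section H for time to discharge, overall and through 7 days:

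1. The log-rank test is stratified by clinical state at entry (ICU, ward on oxygen, ward not on oxygen).
2. The between-group ratio with 95% CI comes from the Cox model of protocol 6.1, stratified by the same factor, and is labelled a subdistribution-type discharge ratio because in-hospital deaths stay at risk to day 28 (or day 7).

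Keep the Kaplan-Meier curves and medians. Region and the pilot indicator can go in a supporting Cox model. Also state that the protocol's Cox models are retained, or list their removal among the exceptions in SAP I.A.

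No new data are needed: entry state is already collected and used in adjacent models. The downside is about 0–2 points of power if entry state turns out not to be prognostic (at most 1.2 in the simulations).

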3.4 Endpoints

The primary endpoint is an ordinal outcome at Day 7 that has 6 mutually exclusive categories:

- 1. death;
- 2. hospitalization in the intensive care unit (ICU);
- 3. non-ICU hospitalizion, requiring supplemental oxygen;
- 4. non-ICU hospitalization, not requiring supplemental oxygen;
- 5. not hospitalized, but unable to resume normal activities; or
- 6. not hospitalized with full resumption of normal activities.

Other endpoints include:

- Change from baseline to Day 3 in NEW score
- The ordinal primary outcome assessed at Days 1-7, 14 and 28
- Number of days hospitalized
- Composite of mortality or hospitalization at Days 7, 14 and 28
- Among those not enrolled in the ICU, requirement for invasive mechanical ventilation or admission to the ICU
- Percent of patients shedding virus at Day 3
- HAI antibody titer changes through Day 7
- Grade 3 and 4 adverse events
- Serious adverse events
- Percent of patients developing bronchitis, pneumonia or other complications through Day 28
- Mortality

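### The time-to-discharge rule credits a readmitted participant who never leaves hospital again with the earlier discharge

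*SAP*

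**What the plan says.** SAP section H lists time to discharge as a supportive efficacy endpoint, compared by a log-rank test. Two periods are analysed: "Kaplan-Meier curves will be used to summarize the time to discharge and time to death, overall and through 7 days".

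Three sentences settle the coding:

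- Deaths: "Deaths during hospitalization will be censored after day 28 (or day 7) for analyses of time to discharge".
- Readmissions: "For participants who experienced multiple hospitalizations during follow-up, the time to the last discharge before day 28 will be considered".
- Late events: because the day 28 visit window runs to day 35, "events after day 28 but prior to the final visit will be included in these analyses".

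None of them makes the event depend on being out of hospital at the end of the period. Protocol section 6.1 does not fill the gap. It specifies Kaplan-Meier plots and Cox models, timed from randomization, and has no readmission rule.

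Readmission and later status are also reported on their own. Section H lists "Percentage alive and out of the hospital at day 28" and "Percentage dying or requiring re-hospitalization after discharge" as further supportive endpoints, and protocol section 3.4 lists "Composite of mortality or hospitalization at Days 7, 14 and 28".

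**The concern.** Using the last discharge rather than the first makes sense if a discharge that does not last should not count. The rule does this for participants who are readmitted and then leave again: their event moves to the later date. It fails for those who are readmitted and do not leave. Their last discharge is the early one, so the discharge that did not last is restored as the event.

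The curve, the median and the log-rank test can therefore count current inpatients as early discharges. If one arm had more readmissions, the curve could hide a difference between the arms in sustained discharge.

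**Working it through.** **The rule applied to example courses (overall analysis)**

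| Course | Literal last-discharge rule | In hospital on day 28 |
|---|---|---|
| Out day 4, not readmitted | event, day 4 | no |
| Out day 4, back day 10, out day 20 | event, day 20 | no |
| Out day 4, back day 10, not out again | event, day 4 | yes |
| One unbroken stay | not discharged | yes |

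The third course is coded like the first, although its status on day 28 is that of the fourth.

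In the 7-day analysis the rule names only day 28. Take a participant who is out on day 3, back on day 6 and out on day 10. Cutting the day-28 rule at day 7 gives not discharged. Moving the limit to day 7, as the death rule does, gives an event at day 3 for someone in hospital on day 7.

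**Size**

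The plan gives no event, power or readmission figure for this endpoint, so there is nothing to reproduce.

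*Inputs from the SAP.* 308 participants are analysed (section D), taken as 154 per arm. 42.0% were discharged by day 3 (Table 5, pooled).

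*Assumptions.* First discharge T is exponential. A share p of discharged participants is readmitted, at a time uniform between T and day 28. The second stay is exponential with a mean of 5 days.

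1. Daily discharge rate: −ln(1 − 0.420)/3 = 0.1816. Check at day 7: 1 − exp(−7 × 0.1816) = 71.9%, against 35.9% + 37.0% = 72.9% in SAP Table 2.
2. Chance that a readmitted participant is in hospital on day 28, given T: [5/(28 − T)] × [1 − exp(−(28 − T)/5)]. At T = 4 this is (5/24) × (1 − exp(−4.8)) = 0.207. Integrated over the density of T from 0 to 28, it is 0.231.
3. Miscoded participants: 308 × p × 0.231. This gives 0.7 at 1%, 1.4 at 2%, 3.6 at 5% and 7.1 at 10%. They are credited with discharge at about day 7 on average.
4. If discharges up to day 35 count and final visits fall on day 35, a share exp(−7/5) = 0.247 remains miscoded: 3.6 × 0.247 = 0.9 at 5% and 7.1 × 0.247 = 1.75 at 10%. If final visits fall on day 28, the figures in step 3 stand.
5. If readmissions come early (mean 7 days after discharge, truncated at day 28), simulation gives about 1.4 miscoded at 5% and 2.8 at 10%.

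**Effect on the test** (simulated, unstratified two-sided log-rank at 0.05)

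- Type 1 error is about 4 to 6% under both the written and the proposed rule. The overall median moves by 0.01 to 0.25 day for readmission from 1% to 15%.
- Suppose readmission is 10% on IVIG and 5% on placebo, with equal first-discharge rates. By actual status, the arms differ on day 28 by 0.231 × (0.10 − 0.05), about 1.1 percentage points. The written rule shows 0.0. Mean log-rank z is −0.73 under the written rule and −0.99 under the proposed one.
- Suppose readmission is unrelated to treatment and the first-discharge rate ratio is 1.40 (assumed, arm rates placed symmetrically about the pooled rate). Power is then as follows; ranges show the spread between simulation runs.

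| Readmission | Written rule | Proposed rule |
|---|---|---|
| 1%, evenly spread | 0.80 | 0.78 |
| 2%, evenly spread | 0.79 | 0.75 |
| 5%, evenly spread | 0.73–0.75 | 0.65–0.66 |
| 10%, evenly spread | 0.65 | 0.53 |
| 5%, early | 0.77–0.78 | 0.74–0.75 |
| 10%, early | 0.71 | 0.65 |

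**The case against.** The strongest reply is that section H already shows what the curve misses. It reports status at days 14 and 28 and death or readmission after discharge, so a reader would see an imbalance directly. That is right, and it is the main reason the point is minor. It does not correct the curve, the median or the test.

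The late-events sentence also helps. If it covers discharges, someone who leaves on day 31 is an event on day 31, and most of the miscoding disappears. That stands as the lower end of the range, but the readmission sentence stops at day 28, so the text does not settle it.

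The proposed rule loses power with no gain in type 1 error. This is also true. The power given up comes only from no longer counting inpatients as discharged.

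Three stronger readings are tempting and are not supported:

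- *A death during a readmission has two equally valid codings.* The death rule is not limited to the first stay, so it naturally covers such a death. Only a statement of precedence is missing.
- *The SAP contradicts itself because the same participant fails the day 28 status endpoint.* Status at day 28 and the protocol composite are separate measures, and disagreement for one participant is not a contradiction. The section G presumption for 4 participants, that "it is presumed that they did not die or were re-hospitalized following discharge", is an imputation for the day 7 favorable outcome and does not define time to discharge.
- *The 7-day and day 35 wording is contradictory.* It is loose. The day 7 limit in the death rule can be carried over to discharges.

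**Conclusion.** Wrong as written; severity minor. The readmission sentence gives a participant who never leaves hospital again a better time than one who is readmitted and later goes home. This follows from the text and needs no assumption.

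The size does rest on assumptions about the rate, timing and length of readmissions, none of which the documents give. At 5% readmission, evenly spread, about 0.9 to 3.6 of 308 participants are affected, and at 10% about 1.75 to 7.1. At 1 to 2% the effect is negligible. A reader might infer a bias in favour of IVIG or a raised false-positive rate. The documents support neither: the rule is the same in both arms and type 1 error is unaffected. The primary day 7 outcome is not touched.

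**What to change.** For each analysis (through 7 days and overall):

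- State one end date.
- Take the last discharge on or before that date, using only data up to it.
- Treat a participant who is in hospital on that date as not discharged, censored there.

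As a clarification only, add that the existing death rule also covers deaths during a readmission and takes precedence over the last-discharge rule.

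This takes two or three sentences and no new data, and it keeps the last-discharge definition. The cost is the power loss tabulated above, if readmission is unrelated to treatment: about 0.02 to 0.04 at 1 to 2% readmission, and 0.07 to 0.10 at 5% when readmissions are evenly spread. It is larger at 10%. Power for the 7-day analysis falls by about 0.02 at most. If the overall end date is day 28, the few discharges between days 28 and 35 are not counted. A pooled, blinded count of participants in hospital on the end date after an earlier discharge would replace the assumed readmission rates.
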